12. ADVERSE EVENT REPORTING

Parents/legally acceptable representatives will receive a study booklet, specifying for both treatment groups important study-related information (see Section 9.6, Study Booklet).

Timely, accurate, and complete reporting and analysis of safety information from clinical studies are crucial for the protection of subjects, investigators, and the sponsor, and are mandated by regulatory agencies worldwide. The sponsor has established Standard Operating Procedures in conformity with regulatory requirements worldwide to ensure appropriate reporting of safety information; all clinical studies conducted by the sponsor or its affiliates will be conducted in accordance with those procedures.

12.1. Definitions

12.1.1. Adverse Event Definitions and Classifications

Adverse Event

An adverse event is any untoward medical occurrence in a clinical study subject administered a medicinal (investigational or non-investigational) product. An adverse event does not necessarily have a causal relationship with the treatment. An adverse event can therefore be any unfavorable and unintended sign (including an abnormal finding), symptom, or disease temporally associated with the use of a medicinal (investigational or non-investigational) product, whether or not related to that medicinal (investigational or non-investigational) product. (Definition per International Conference on Harmonisation [ICH])

This includes any occurrence that is new in onset or aggravated in severity or frequency from the baseline condition, or abnormal results of diagnostic procedures, including laboratory test abnormalities.

Note: The sponsor collects adverse events starting with the signing of the ICF (refer to Section 12.3.1, All Adverse Events, for time of last adverse event recording).

Serious Adverse Event

A serious adverse event based on ICH and EU Guidelines on Pharmacovigilance for Medicinal Products for Human Use is any untoward medical occurrence that at any dose:

- Results in death
- Is life-threatening
(The subject was at risk of death at the time of the event. It does not refer to an event that hypothetically might have caused death if it were more severe.)
- Requires inpatient hospitalization or prolongation of existing hospitalization
- Results in persistent or significant disability/incapacity

- Is a congenital anomaly/birth defect
- Is a suspected transmission of any infectious agent via a medicinal product
- Is Medically Important*

*Medical and scientific judgment should be exercised in deciding whether expedited reporting is also appropriate in other situations, such as important medical events that may not be immediately life threatening or result in death or hospitalization but may jeopardize the subject or may require intervention to prevent one of the other outcomes listed in the definition above. These should usually be considered serious.

For the purposes of this study, efficacy outcome events (thrombotic events) will not be reported as adverse events or serious adverse events, as they will be reported as efficacy outcomes (See Section 12.3.1, All Adverse Events.).

Serious bleeding events will be considered serious adverse events and must be reported to the sponsor in an expedited manner as any other serious adverse events.

If a serious and unexpected adverse event occurs for which there is evidence suggesting a causal relationship between the study drug and the event, the event must be reported by the sponsor as a serious and unexpected suspected adverse reaction even if it is a component of the study endpoint.

Unlisted (Unexpected) Adverse Event/Reference Safety Information

An adverse event is considered unlisted if the nature or severity is not consistent with the applicable product reference safety information. For rivaroxaban, the expectedness of an adverse event will be determined by whether or not it is listed in the Investigator's Brochure.

Adverse Event Associated With the Use of the Drug

An adverse event is considered associated with the use of the drug if the attribution is possible, probable, or very likely by the definitions listed below in Section 12.1.2, Attribution Definitions.

12.1.2. Attribution Definitions

Not Related

An adverse event that is not related to the use of the drug.

Doubtful

An adverse event for which an alternative explanation is more likely, eg, concomitant drug(s), concomitant disease(s), or the relationship in time suggests that a causal relationship is unlikely.

Possible

An adverse event that might be due to the use of the drug. An alternative explanation, eg, concomitant drug(s), concomitant disease(s), is inconclusive. The relationship in time is reasonable; therefore, the causal relationship cannot be excluded.

Probable

An adverse event that might be due to the use of the drug. The relationship in time is suggestive (eg, confirmed by dechallenge). An alternative explanation is less likely, eg, concomitant drug(s), concomitant disease(s).

Very Likely

An adverse event that is listed as a possible adverse reaction and cannot be reasonably explained by an alternative explanation, eg, concomitant drug(s), concomitant disease(s). The relationship in time is very suggestive (eg, it is confirmed by dechallenge and rechallenge).

12.1.3. Severity Criteria

An assessment of severity grade will be made using the following general categorical descriptors:

Mild: Awareness of symptoms that are easily tolerated, causing minimal discomfort and not interfering with everyday activities.

Moderate: Sufficient discomfort is present to cause interference with normal activity.

Severe: Extreme distress, causing significant impairment of functioning or incapacitation. Prevents normal everyday activities.

The investigator should use clinical judgment in assessing the severity of events not directly experienced by the subject (eg, laboratory abnormalities).

12.2. Special Reporting Situations

Safety events of interest on a sponsor study drug that may require expedited reporting and/or safety evaluation include, but are not limited to:

- Overdose of a sponsor study drug
- Suspected abuse/misuse of a sponsor study drug
- Accidental or occupational exposure to a sponsor study drug
- Any failure of expected pharmacologic action (ie, lack of effect) of a sponsor study drug
- Unexpected therapeutic or clinical benefit from use of a sponsor study drug
- Medication error involving product preparation or dose administration of a sponsor product (with or without subject/patient exposure to the sponsor study drug, eg, name confusion)

Special reporting situations should be recorded in the eCRF. Any special reporting situation that meets the criteria of a serious adverse event should be recorded on the serious adverse event page of the eCRF

12.3. Procedures

12.3.1. All Adverse Events

Adverse events should be reported by the subjects or their parents/legally acceptable representatives for the duration of the study.

For the purposes of this study, thrombotic events will be captured in the eCRF and in the database as efficacy outcomes only, and will not be reported as adverse events or serious adverse events, regardless of seriousness and severity, except for those thrombotic events that ended in death. All other thrombotic events will be exempted from expedited reporting.

Any serious adverse events other than thrombotic events will be reported to the sponsor in an expedited fashion according to Section 12.3.2, Serious Adverse Events.

All deaths (including those due to thrombotic causes) will be reported as serious adverse events.

All bleeding events will be collected on the eCRF as a bleeding event and as an adverse event or serious adverse event as appropriate. Serious bleeding events must be reported to the sponsor in an expedited manner as any other serious adverse events.

Certain adverse events are considered to be Adverse Events of Special Interest and should be reported as serious adverse events. These include:

- Suspected toxic effect on the bone marrow including severe thrombocytopenia (platelet count less than $50 \times 10^9/L$), severe neutropenia (white blood cell count less than $500/\mu L$), pancytopenia, aplastic anemia
- Suspected severe hypersensitivity reaction (eg, anaphylaxis, angioedema, severe urticaria, bronchospasm, etc.)
- Severe skin reactions such as Stevens-Johnson Syndrome
- Suspected severe liver injury and concurrent elevations of ALT $>5x$ ULN and total bilirubin $>2x$ ULN

All adverse events and special reporting situations, whether serious or nonserious, will be reported from the time a signed and dated ICF is obtained until completion of the subject's last study-related procedure (ie, Follow-Up Contact [phone contact]).

Serious adverse events, including those spontaneously reported to the investigator within 30 days after the last dose of study drug, must be reported via facsimile (fax) when applicable using the Serious Adverse Event page of the eCRF. The sponsor will evaluate any safety information that is spontaneously reported by an investigator beyond the time frame specified in the protocol.

All adverse events, regardless of seriousness, severity, or presumed relationship to study drug, must be recorded using medical terminology in the source document and the eCRF. Whenever possible, diagnoses should be given when signs and symptoms are due to a common etiology (eg, cough, runny nose, sneezing, sore throat, and head congestion should be reported as "upper

respiratory infection"). Investigators must record in the eCRF their opinion concerning the relationship of the adverse event to study therapy. All measures required for adverse event management must be recorded in the source document and reported according to sponsor instructions.

The sponsor assumes responsibility for appropriate reporting of adverse events to the regulatory authorities. The sponsor will also report to the investigator (and the head of the investigational institute where required) all suspected unexpected serious adverse reactions (SUSARs). The investigator (or sponsor where required) must report SUSARs to the appropriate Independent Ethics Committee/Institutional Review Board (IEC/IRB) that approved the protocol unless otherwise required and documented by the IEC/IRB. A SUSAR will be reported to regulatory authorities unblinded. Participating investigators and IEC/IRB will receive a blinded SUSAR summary, unless otherwise specified.

For all studies with an outpatient phase, including open-label studies, parent/legally acceptable representative must be provided with a "wallet (study) card" and instructed to carry this card with them for the duration of the study indicating the following:

- Study number
- Statement, in the local language(s), that the subject is participating in a clinical study
- Investigator's name and 24-hour contact telephone number
- Local sponsor's name and 24-hour contact telephone number (for medical staff only)
- Site number
- Subject number
- Any other information that is required to do an emergency breaking of the blind

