- i) Minimum criteria for the availability of documentation supporting the eligibility criteria are described in Section 17.4, Source Documentation. Check clinical status again before first dose of study medication.
- j) Subjects will be enrolled and randomized on Visit 2/Day 1 after meeting inclusion and exclusion criteria. Subjects may be enrolled and randomized on the business day prior to Day 1 to facilitate logistics provided the investigator ensures that the subject meets all eligibility criteria prior to randomization. The first dose of study drug will be administered on site on Day 1 if the subject is still eligible.
- k) For subjects randomized to rivaroxaban, the AM dose will be administered at the site.
- l) If a suspected outcome event (thrombotic or bleeding event) occurs, the adjudication package is to be completed.
- m) Only vital status and thrombotic events (no bleeding events) will be assessed and an adjudication package will be completed.
- n) Adverse event assessment includes a review of all ongoing and new adverse events since the last visit for all visits through Month 12.
- o) Physical examination of the subject will be symptom-driven.
- p) Transthoracic echocardiograms will be obtained at screening, Month 6 and Month 12, or ESMD and whenever medically necessary, and results sent to core laboratory. For screening see footnote 'a'.
- q) Hematology (complete blood count [CBC] with differential, platelet count); blood chemistry (liver function tests [alanine aminotransferase, ALT; aspartate aminotransferase, AST; total and direct bilirubin, alkaline phosphatase] and creatinine).
- r) Hematology and serum chemistry testing at screening (testing should be done after the Fontan procedure and results should be available within 21 days prior to randomization, at Month 12 and ESMD visit). Note: Hospital laboratory, local laboratory results or central laboratory results are acceptable at screening, and the most recent clinical laboratory results will be used for screening if there are multiple laboratory results.
- s) If a subject experiences a major bleeding event while being treated with rivaroxaban, obtain PK and PD samples (see also Section 9.3.2 for approach to the subject with a bleeding event and Section 9.5 for sample instructions).
- t) To be collected at any timepoint during the visit (PK, PT, and aPTT). Parent/legally acceptable representative should document timing of the administered AM study drug dose.

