9.3.3. Other Safety Assessments

The safety and tolerability of rivaroxaban will also be evaluated by assessing other adverse events and clinical laboratory test values.

Any clinically relevant changes, including laboratory reports, occurring during the study must be recorded on the Adverse Event section of the eCRF. Any clinically significant abnormalities persisting at the end of the study/early withdrawal will be followed by the investigator until resolution or until a clinically stable endpoint is reached.

The study includes the evaluations of safety and tolerability according to the time points provided in the Time and Events Schedule.

Adverse Events

Adverse events will be reported by the parents/legally acceptable representatives for the duration of the study up to the Follow-Up Contact (30-days after last dose). Adverse events will be followed by the investigator as specified in Section 12, Adverse Event Reporting.

Clinical Laboratory Tests

The following tests results with reference ranges will be obtained at the visits specified in the Time and Events Schedule. Either hospital laboratory/local laboratory results or central laboratory results are acceptable at the time of study screening period. A central laboratory will be used during the rest of the study:

- Hematology Panel
 - hemoglobin
 - hematocrit
 - red blood cell (RBC) count^a
 - white blood cell (WBC)^b count
 - WBC differential^b:
 - neutrophils
 - lymphocytes
 - monocytes
 - eosinophils
 - basophils
 - platelet count
- Serum chemistry
 - creatinine (eGFR will be calculated using the original or the modified Schwartz formula for pediatric population, see [Attachment 3](#))²⁹
 - liver function tests (ALT, aspartate aminotransferase [AST], total and direct bilirubin, alkaline phosphatase)
- PT, aPTT tests

^a A RBC evaluation may include abnormalities in RBC count and/or RBC parameters (eg, reticulocyte count) and/or RBC morphology, which will then be reported by the laboratory

^b A WBC evaluation may include any abnormal cells, which will then be reported by the laboratory. In addition, any other abnormal cells in a blood smear will also be reported.

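### The special-interest event severe neutropenia has its numeric criterion set on total white cells rather than neutrophils, so isolated neutropenia cannot meet it

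*Protocol*

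**What the plan says.** Protocol section 12.3.1 states: "Certain adverse events are considered to be Adverse Events of Special Interest and should be reported as serious adverse events". The first item opens "Suspected toxic effect on the bone marrow including severe thrombocytopenia (platelet count less than" 50 × 10⁹/L), continues with "severe neutropenia (white blood cell count less than" 500/µL), and then names pancytopenia and aplastic anemia without a figure.

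Section 9.3.3 lists the hematology panel. It has one line for "white blood cell (WBC)^b count" and a separate line for "WBC differential^b", under which neutrophils are the first of five cell types. The footnotes to the Time and Events Schedules for both parts describe the test as "Hematology (complete blood count [CBC] with differential, platelet count", so a neutrophil count is available whenever hematology is done under the protocol.

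Nothing else in the protocol gives a neutrophil-based definition. The SAP neither defines nor summarizes events of special interest (SAP 4.2).

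**The concern.** The term and the measured quantity do not match. In the same item, severe thrombocytopenia is defined by the platelet count, which is its own cell line. Only the neutropenia entry is tied to a broader quantity than the one it names.

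The entry is operational. Meeting it obliges the site to file a serious adverse event report, which section 12.3.2 requires within 24 hours. Section 3.1 names serious adverse events among the incidences that the data monitoring committee reviews regularly. A site applying the number literally would conclude that a child with very few neutrophils but ordinary lymphocytes does not qualify.

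The remaining safeguards contain no neutrophil figure. Section 12.1.3 grades severity by general descriptors and leaves laboratory abnormalities to clinical judgment. SAP 4.3 plans only descriptive laboratory statistics by group and time point, which can hide one child's abnormal value. In an open-label trial, reporting that rests on judgment may also differ between arms.

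**Working it through.** The plan gives no figure to reproduce here. The check is on the logic of the criterion.

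**Inputs**
- Written criterion: white cell count (WBC) < 500/µL (Protocol 12.3.1).
- Neutrophils are a component of WBC (Protocol 9.3.3).
- Scheduled hematology: screening, Month 12 and the early discontinuation (ESMD) visit (Time and Events Schedules, Parts A and B). Attachment 1 budgets 2 hematology samples per child in each part.

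**Step 1: how the two criteria relate.** Let N be the neutrophil count and L all other white cells, so WBC = N + L.
- Written criterion: N + L < 500.
- Same figure applied to the named quantity: N < 500.
- Since L ≥ 0, the first implies the second but not the reverse. If L ≥ 500, then N + L ≥ 500 even at N = 0, so the written criterion cannot be met.

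**Step 2: illustrations (not trial data).**

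| WBC (/µL) | Neutrophils | N (/µL) | N < 500? | Written criterion met? |
|---|---|---|---|---|
| 400 | 10% | 40 | yes | yes |
| 1,000 | 20% | 200 | yes | no |
| 2,000 | 10% | 200 | yes | no |
| 3,000 | 10% | 300 | yes | no |
| 5,000 | 5% | 250 | yes | no |

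In the fourth row, 3,000 × 0.10 = 300, while 3,000 / 500 = 6 times the written limit.

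**Step 3: can the affected share be stated?** Not from the documents, which give no leukocyte distribution. As a sensitivity check only, assume N is uniform on 0–500/µL and L is lognormal with log-SD 0.4 to 0.8. The simulated share of N < 500 cases that fall outside the written criterion is:

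| Assumed median L (/µL) | Share outside |
|---|---|
| 100 | 22–27% |
| 200 | 43–48% |
| 250 | 53–55% |
| 300 | 62–63% |
| 500 | 79–88% |
| 1,000 | 94–99% |
| 2,000 or more | 99–100% |

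A hand check agrees. If L is fixed at a value below 500, the share is L/500: 100/500 = 20% and 250/500 = 50%. The result runs from about a fifth to essentially all, depending wholly on the assumed L.

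**Step 4: scheduled exposure.** 2 budgeted samples − 1 at screening = 1 scheduled post-baseline count per child, at Month 12 or ESMD. The Month 3 laboratory visit in Part A is chemistry only. Attachment 1 also allows unscheduled samples for safety reasons, and those are outside this count.

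**The case against.** The strongest reply is that the number is not the rule. The item covers any suspected toxic effect on the marrow, and the cytopenias are introduced as inclusions, so the list is not exhaustive. An investigator who suspects marrow toxicity at 300 neutrophils/µL can report it without meeting the white-cell figure. Pancytopenia and aplastic anemia, which carry no figure, cover many multi-lineage cases.

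Other routes remain. Section 12.1.1 has the serious criterion "Is Medically Important", and hospitalization is another. Section 12.3.1 also requires that "All adverse events, regardless of seriousness, severity, or presumed relationship to study drug, must be recorded", section 9.3.3 sends clinically relevant laboratory changes to the adverse event pages, and section 17.6 has central laboratory data passing directly to the sponsor. The monitoring committee's remit in section 9.7.2 covers safety data generally. Neutropenia and marrow toxicity are not among the adverse reactions listed in section 1.1.3, and no planned safety or efficacy estimate uses this threshold.

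All of this stands, and it limits the consequence. A reader might infer that most true severe neutropenia would go unreported, or that marrow signals would be lost. The documents do not support either reading. The word *most* needs a leukocyte distribution that they do not give, and what is lost is automatic qualification, not the record of the event.

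The reply does not remove the mismatch. The serious-event fallbacks rest largely on judgment, and a stated number exists so that sites need not rely on judgment alone. No other text corrects this one.

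**Conclusion.** Wrong as written, minor severity. The numeric criterion for severe neutropenia is a strict subset of the same figure applied to neutrophils, and no child with at least 500/µL of other white cells can meet it. That much follows from arithmetic and needs no assumption.

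The consequence is narrow: such a case does not automatically qualify for serious-event reporting through the number. It may still be reported by judgment, and it would be recorded as an ordinary adverse event. The shares in the working rest on assumed distributions and should not be cited as an estimate for this trial. How often the situation would arise is unknown. With one scheduled post-baseline count per child, at or near the end of treatment, unscheduled counts are the other place where the criterion would be applied.

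**What to change.** In section 12.3.1, reconcile the term with the laboratory quantity so that the neutropenia criterion refers to the neutrophil count from the differential. The sponsor should confirm the threshold: the documents state 500/µL only for total white cells, so carrying that figure over to neutrophils is an inference. Any site or eCRF instruction that repeats the wording should be aligned; the documents do not describe a specific eCRF check on this value.

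The cost is one phrase. The differential is already collected in both parts, so no new test or blood volume is needed. The downside is possibly a few more special-interest reports.

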12.3.2. Serious Adverse Events

All serious adverse events occurring during the study must be reported to the appropriate sponsor contact person by study-site personnel within 24 hours of their knowledge of the event.

Information regarding serious adverse events will be transmitted to the sponsor using the Serious Adverse Event page of the eCRF, which must be completed and signed by a physician from the study site, and transmitted to the sponsor within 24 hours. The initial and follow-up reports of a serious adverse event should be transmitted electronically via facsimile (fax).

All serious adverse events that have not resolved by the end of the study, or that have not resolved upon discontinuation of the subject's participation in the study, must be followed until any of the following occurs:

- The event resolves
- The event stabilizes
- The event returns to baseline, if a baseline value/status is available

- The event can be attributed to agents other than the study drug or to factors unrelated to study conduct
- It becomes unlikely that any additional information can be obtained (subject or health care practitioner refusal to provide additional information, lost to follow-up after demonstration of due diligence with follow-up efforts)

Suspected transmission of an infectious agent by a medicinal product will be reported as a serious adverse event.

Any event requiring hospitalization (or prolongation of hospitalization) that occurs during the course of a subject's participation in a study must be reported as a serious adverse event, except hospitalizations for the following:

- For the purposes of this study, thrombotic events will not be reported as serious adverse events, refer to Section 12.3.1, All Adverse Events for details.
- Hospitalizations not intended to treat an acute illness or adverse event (eg, social reasons such as pending placement in long-term care facility)
- Surgery or procedure planned before entry into the study (must be documented in the eCRF). Note: Hospitalizations that were planned before the signing of the ICF, and where the underlying condition for which the hospitalization was planned has not worsened, will not be considered serious adverse events. Any adverse event that results in a prolongation of the originally planned hospitalization is to be reported as a new serious adverse event.

The cause of death of a subject in a study, whether or not the event is expected or associated with the study drug, is considered a serious adverse event.

